| Table I – 8 CD4+ T cells
cytokines including IFN-γ   | expressing at le
: Descriptive st                                     | east 2
atistics     | Template Table
I - 3  |                                 | Supplementary
Table I.2-8     | %CMI      |
| Table I – 9 CD4+ T cells
cytokines including CD40
statistics  | expressing at le
)-L : Descriptive                                    | east 2                 | Template Table
I - 3  |                                 | Supplementary
Table I.2-9     | %CMI      |
| Table I – 10 CD4+ T cells
cytokines : Descriptive st   | expressing at latistics  | least 2                | Template Table
I - 3  |                                 | Supplementary
Table I.2-10    | %CMI      |
| 3.1.3. Exploratory object
Table I – 1b Frequency of
expressing cytokines (by
vaccination: percentilos) | f CD8+ T-cells
ICS) at pre-   |                        | Template Table
I - 1  |                                 | Working Table
I.2-1b          | Specific  |
| Table I – 11 CD8+ T cells
one cytokine (TNF-α and
statistics (amendment 1                                 | s expressing at l
I/or IFN-γ) : Des                                   | least
scriptive     | Template Table
I - 3  |                                 | Supplementary
Table I.2-11    | %CMI      |
| Table I – 12 CD8+ T cells
α : Descriptive statistics   | s expressing on
amendment 1)  | ly TNF-                | Template Table
I - 3  |                                 | Supplementary
Table I.2-12    | %CMI      |

| gsk
GlaxoSmithKline   | Study RAP   |                         |                   |                        |                                  |          |
|--|-------------|-------------------------|-------------------|------------------------|----------------------------------|----------|
| Study Id: 108706   | A           | breviated Tit           | le:               | PRO I                  | HIV-005                          |          |
| Version: Draft version   | X           | Final                   |                   | Date:                  | 26SEP 2008                       |          |
|  |             | CONFIDENTI              | AL                |                        |                                  |          |
| Denomination   |             | Template table          | To
vacci
co | otal
inated
hort | ATP cohort for
immunogenicity | Macro    |
| Table I – 13 CD8+ T cells expressing only IF
: Descriptive statistics (amendment 1)   | Ν- γ | Template Table
I - 3 |                   |                        | Supplementary
Table I.2-13    | %CMI     |
| Table I – 14 CD8+ T cells expressing TNF-α
and IFN-γ : Descriptive statistics (amendme
1)  | nt          | Template Table
I - 3 |                   |                        | Supplementary
Table I.2-14    | %CMI     |
| Table I – 16 CD8+ T cells expressing at least
one cytokine (TNF-α and/or IFN-γ) : Number
and percentage of responders per antigen
(amendment 1)         | :
r      | Template Table
I - 4 |                   |                        | Table I.2-16                     | Specific |
| Table I – 17 CD4+ T cells expressing at least 2 cytokines including IL-2 (stimulaled with other HIV clade antigens) : Descriptive statistics                     |             | Template Table
I - 3 |                   |                        | Table I.2-17                     | %CMI     |
| Table I – 18 CD4+ T cells expressing at least
cytokines including TNF-α (stimulaled with ot
HIV clade antigens): Descriptive statistics                    | 2
her    | Template Table
I - 3 |                   |                        | Supplementary
Table I.2-18    | %CMI     |
| Table I – 19 CD4+ T cells expressing at least
cytokines including IFN-γ (stimulaled with oth
HIV clade antigens): Descriptive statistics                   | :2
er    | Template Table
I - 3 |                   |                        | Supplementary
Table I.2-19    | %CMI     |
| Table I – 20 CD4+ T cells expressing at least
cytokines including CD40-L (stimulaled with
other HIV clade Table I.2-4.antigens):
Descriptive statistics | 2           | Template Table
I - 3 |                   |                        | Supplementary
Table I.2-20    | %CMI     |
| Table I – 21 CD4+ T cells expressing at least
cytokines (stimulaled with other HIV clade
antigens): Descriptive statistics                                 | 2           | Template Table
I - 3 |                   |                        | Supplementary
Table I.2-21    | %CMI     |
| 3.2. Antibodies by Elisa   |             |                         |                   |                        |                                  |          |
| Table I - 22 Seroposivity rates and GMTs for
antibodies   | •           | Template Table
I - 7 |                   |                        | Table I.2-22                     | %GMT     |

| gsk
GlaxoSmithKline | Stu                | Study RAP        |  |  |
|------------------------|--------------------|------------------|--|--|
| Study Id: 108706       | Abbreviated Title: | PRO HIV-005      |  |  |
| Version: Draft version | ⊠ Final            | Date: 26SEP 2008 |  |  |

#### 5.3. Template of tables

#### 5.3.1. Study cohorts and demography analysis

#### 5.3.1.1. Study cohorts

Template Table D - 1 Number of subjects enrolled into the study as well as the number of subjects excluded from ATP analyses with reasons for exclusion

|                           | Total |   |   | [Each group] |   |
|---------------------------|-------|---|---|--------------|---|
| Title                     | n     | S | % | n            | s |
| Total enrolled cohort     |       |   |   |              |   |
| (code XXXX)               |       |   |   |              |   |
| Total vaccinated cohort   |       |   |   |              |   |
| (code XXXX)               |       |   |   |              |   |
| ATP safety cohort         |       |   |   |              |   |
| (code XXXX)               |       |   |   |              |   |
| ATP immunogenicity cohort |       |   |   |              |   |

Note: Subjects may have more than one elimination code assigned

n = number of subjects with the elimination code assigned excluding subjects who have been assigned a lower elimination code number

s = number of subjects with the elimination code assigned

% = percentage of subjects in the considered ATP cohort relative to the Total vaccinated cohort Data source = Appendix table IA

| gsk
GlaxoSmithKline | Stu                | Study RAP        |  |  |
|------------------------|--------------------|------------------|--|--|
| Study Id: 108706       | Abbreviated Title: | PRO HIV-005      |  |  |
| Version: Draft version | n 🗵 Final          | Date: 26SEP 2008 |  |  |
|                        |                    |                  |  |  |

Template Table D - 2

Number of subjects at each visit and list of withdrawn subjects

| Group        | VISIT    | N | Withdrawn
Subject numbers | Reason for withdrawal |  |
|--------------|----------|---|------------------------------|-----------------------|--|
| [Each group] | VISIT 1  |   |                              |                       |  |
|              | VISIT 2  |   |                              |                       |  |
|              | VISIT 3  |   |                              |                       |  |
|              | VISIT 4  |   |                              |                       |  |
|              | VISIT 5  |   |                              |                       |  |
|              | VISIT 6  |   |                              |                       |  |
|              | VISIT 7  |   |                              |                       |  |
|              | VISIT 8  |   |                              |                       |  |
|              | VISIT 9  |   |                              |                       |  |
|              | VISIT 10 |   |                              |                       |  |

Data source = Appendix table IC, Appendix table IEi

#### Template Table D - 3

## Number of subjects vaccinated, completed and withdrawn with reason for withdrawal

|   | [Each group] | Total |
|---|--------------|-------|
| Number of subjects enrolled                                     |              |       |
| Number of subjects completed                                    |              |       |
| Number of subjects withdrawn                                    |              |       |
|   |              |       |
| Reasons for withdraw:   |              |       |
| Serious Adverse Event   |              |       |
| Non-serious adverse event                                       |              |       |
| Protocol violation  |              |       |
| Consent withdrawal (not due to an adverse event)                |              |       |
| Migrated/moved from study area                                  |              |       |
| Lost to follow-up (subjects with incomplete vaccination course) |              |       |
| Lost to follow-up (subjects with complete vaccination course)   |              |       |
| Others  |              |       |

Vaccinated = number of subjects who were vaccinated in the study Completed = number of subjects who completed last study visit Withdrawn = number of subjects who did not come for the last visit Data source = Appendix table IEi

#### Template Table D - 4

#### Minimum and maximum activity dates

| Activity number |              | Minimum date | Maximum date |
|-----------------|--------------|--------------|--------------|
| [Each activity] | [Each visit] | DDMMMYYYY    | DDMMMYYYY    |
|                 |              | DDMMMYYYY    | DDMMMYYYY    |

| gsk
GlaxoSmithKline | Stu                | dy RAP           |
|------------------------|--------------------|------------------|
| Study Id: 108706       | Abbreviated Title: | PRO HIV-005      |
| Version: Draft version | ⊠ Final            | Date: 26SEP 2008 |
|                        | CONFIDENTIAL       |                  |

Template Table D - 5

Number and percentage of subjects who received the vaccine dose(s)

|     | [Each group]
(N =) |   | To
(N | ital
  =) |
|-----|-----------------------|---|----------|--------------|
|     | n                     | % | n        | %            |
| 1   |                       |   |          |              |
| 2   |                       |   |          |              |
| Any |                       |   |          |              |

N = number of subjects in each group or in total included in the considered cohort

n/% = number/percentage of subjects receiving the specified total number of doses in each group or in total

Any = number and percentage of subjects receiving at least one dose

Data source = Appendix table IG, Appendix table IIA, Appendix table IIB

## Template Table D - 6 Deviations from specifications for age and intervals between study visits

|              |       | Age           | VISIT 1 – VISIT 2 | [Other intervals]  |
|--------------|-------|---------------|-------------------|--------------------|
| Group        |       | Protocol      | Protocol          | Protocol           |
|              |       | from xx to xx | From 0 to 0 days  | from xx to xx days |
|              |       |               |                   |                    |
| [Each group] | Ν     |               |                   |                    |
|              | n     |               |                   |                    |
|              | %     |               |                   |                    |
|              | range |               |                   |                    |

Adapted = interval used for defining the ATP cohorts for immunogenicity

N = total number of subjects with available results

n/% = number / percentage of subjects with results outside of the interval

range = minimum-maximum for age and intervals

Data source = Appendix table IB, Appendix table ICi

| gsk
GlaxoSmithKline | St                 | Study RAP        |  |  |
|------------------------|--------------------|------------------|--|--|
| Study Id: 108706       | Abbreviated Title: | PRO HIV-005      |  |  |
| Version: Draft vers    | sion 🛛 🖾 Final     | Date: 26SEP 2008 |  |  |

#### 5.3.1.2. **Demographic characteristics**

Template Table D - 7

#### Summary of demographic characteristics

|                 | Parameters or   |               | [Each group]
N= |               | al
: |
|-----------------|---|---------------|--------------------|---------------|---------|
| Characteristics | Categories  | Value or
n | %                  | Value
or n | %       |
| Age(Years)      | Mean
SD
Median
Minimum
Maximum  |               |                    |               |         |
| Gender          | Female
Male  |               |                    |               |         |
| Race            | African Heritage / African American
American Indian or Alaskan Native
Asian – Central / South Asian Heritage
Asian – East Asian Heritage
Asian – Japanese Heritage
Asian – South East Asian Heritage
Native Hawaiian or Other Pacific Islander
White – Arabic / North African Heritage
White – Caucasian / European Heritage
Other |               |                    |               |         |

N = number of subjects

n = number of subjects in a given category Value = value of the considered parameter

% = n/Number of subjects with available results x 100

Data source = Appendix table IB

| gsk
GlaxoSmithKline | Study RAP         |                  |  |  |  |  |
|------------------------|-------------------|------------------|--|--|--|--|
| Study Id: 108706       | Abbreviated Title | PRO HIV-005      |  |  |  |  |
| Version: Draft version | n 🛛 Final         | Date: 26SEP 2008 |  |  |  |  |

#### 5.3.2. Reactogenicity/Safety

#### 5.3.2.1. Compliance with respect to documenting safety

Template Table R - 1 Compliance in returning symptom sheets

| Dose   | Group        | Number
Of
Doses | Doses
NOT
according
to protocol | Number
Of
General SS | Compliance
%
general | Number
Of
Local SS | Compliance
%
Local |
|--------|--------------|-----------------------|--|----------------------------|----------------------------|--------------------------|--------------------------|
| 1
2 | [Each group] |                       |  |                            |                            |                          |                          |
| Total  |              |                       |  |                            |                            |                          |                          |

SS = Symptom sheets used for the collection of local and general solicited AEs Compliance % = (number of doses with symptom sheet returned / number of administered doses) X 100 Data source = Appendix table IG, Appendix table IIA, Appendix table IIB

#### Template Table R - 2

Compliance to data capture

|              |                                       | [Each dose] |   | All doses |   | Per subject |   |
|--------------|---------------------------------------|-------------|---|-----------|---|-------------|---|
| Group        | Criteria                              | n           | % | n         | % | n           | % |
| [Each group] | With visit done                       |             |   |           |   |             |   |
|              | With dose received                    |             |   |           |   |             |   |
|              | With local solicited data available   |             |   |           |   |             |   |
|              | With general solicited data available |             |   |           |   |             |   |
| Total        | With visit done                       |             |   |           |   |             |   |
|              | With dose received                    |             |   |           |   |             |   |
|              | With local solicited data available   |             |   |           |   |             |   |
|              | With general solicited data available |             |   |           |   |             |   |

n = for each dose: number of subjects enrolled in the considered cohort and fulfilling specific criteria for the considered dose for all doses : sum of n from individual doses

per subject : number of subjects enrolled in the considered cohort and fulfilling specific criteria for at least one dose % = percentage of doses with solicited/unsolicited data available among the number of administered doses Data source = Appendix table IG

| gsk
GlaxoSmithKline | Study RAP          |                  |  |  |  |
|------------------------|--------------------|------------------|--|--|--|
| Study Id: 108706       | Abbreviated Title: | PRO HIV-005      |  |  |  |
| Version: Draft version | ⊠ Final            | Date: 26SEP 2008 |  |  |  |
|                        |                    |                  |  |  |  |

#### 5.3.2.2. All symptoms

Template Table R - 3

Incidence and nature of symptoms reported during the 7-day (Days 0-6) post-vaccination period

|              | Any Symptom  |   |   |   | General symptoms |      |   |   | Local symptoms |     |      |   |   |   |     |      |
|--------------|--------------|---|---|---|------------------|------|---|---|----------------|-----|------|---|---|---|-----|------|
|              | Group        | Ν | n | % | 95%              | 6 CI | Ν | n | %              | 95% | 6 CI | Ν | n | % | 95% | 6 CI |
|              |              |   |   |   | LL               | UL   |   |   |                | LL  | UL   |   |   |   | LL  | UL   |
| Dose 1       | [Each group] |   |   |   |                  |      |   |   |                |     |      |   |   |   |     |      |
| Dose 2       | [Each group] |   |   |   |                  |      |   |   |                |     |      |   |   |   |     |      |
| Overall/dose | [Each group] |   |   |   |                  |      |   |   |                |     |      |   |   |   |     |      |
| Overall/subj | [Each group] |   |   |   |                  |      |   |   |                |     |      |   |   |   |     |      |

For each dose and overall/subject:

N= number of subjects with at least one documented dose

n/%= number/percentage of subjects presenting at least one type of symptom whatever the study vaccine administered For overall/dose:

N= number of documented doses

n/%= number/percentage of doses followed by at least one type of symptom whatever the study vaccine administered 95% CI = exact 95% confidence interval, LL = Lower Limit, UL = Upper Limit

Data source = Appendix table IIA, Appendix table IIB

| gsk
GlaxoSmithKline | Study RAP          |                  |  |  |  |  |
|------------------------|--------------------|------------------|--|--|--|--|
| Study Id: 108706       | Abbreviated Title: | PRO HIV-005      |  |  |  |  |
| Version: Draft version | n 🛛 Final          | Date: 26SEP 2008 |  |  |  |  |
|                        |                    |                  |  |  |  |  |

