10.6. Derived and transformed data

Serology data

- The cut-off values for antibody titers will be defined by the laboratory before the analysis.
- A seronegative subject is a subject whose titer is below the cut-off value.
- A seropositive subject is a subject whose titer is greater than or equal to the cut-off value.
- The seropositivity rate is defined as the percentage of seropositive subjects.
- The Geometric Mean Titers (GMTs) calculations will be performed by taking the anti-log of the mean of the log titer transformations. Antibody titers below the cut-off of the assay will be given an arbitrary value of half the cut-off for the purpose of GMT calculation.

JCS data

- ICS data will be expressed as antigen-specific CD4/CD8 T-cells per million respectively of CD4 or CD8+ T-cells.
- The cut-off will be calculated by taking the 95 percentile of the pre-vaccination data of all subjects.
- A responder is a subject with antigen-specific CD4/CD8 T-cells response greater than or equal to the cut-off value.
- Frequency of CD4/CD8 T-cells expressing cytokines to the fusion protein F4co (all antigens) will be estimated by adding individual frequencies of CD4/CD8 T-cells to each 4 antigens (p17, p24, Nef, RT).

Handling of missing

- For a given subject and a given immunogenicity measurement, missing or nonevaluable measurements will not be replaced.
- For the calculation of percentage of responders to 1, 2, 3 and all 4 antigens, subjects not responding to at least one of the concerned antigen(s) will not be taken into account.
- For the analysis of solicited symptom, missing or non-evaluable measurements will not be replaced. Therefore the analysis of the solicited symptoms based on the total

vaccinated cohort will include only injections with documented safety data (i.e. symptom screen/sheet completed).

• For the analysis of unsolicited adverse events/serious adverse event/concomitant medication, all vaccinated subjects will be considered and subjects who did not report an event will be considered as subjects without an event.

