## 3.2.2. Handling of missing data

For the analysis of solicited symptoms, missing or non-evaluable measurements will not be replaced. Therefore the analysis of the solicited symptoms based on the

| gsk
GlaxoSmithKline | Study RAP          |                  |
|------------------------|--------------------|------------------|
| Study Id: 108706       | Abbreviated Title: | PRO HIV-005      |
| Version: Draft version | on 🛛 Final         | Date: 26SEP 2008 |

totalvaccinated cohort will include only subjects/doses with documented safety data (i.e.symptom screen/sheet completed).

For the analysis of unsolicited adverse events/serious adverse event/concomitant medication, all vaccinated subjects will be considered and subjects who did not report an event will be considered as subjects without an event.

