## 3.2.4. All symptoms

This analysis will be performed for Month 2 only.

The percentage of subjects with at least one local AE (solicited and unsolicited), with at least one general AE (solicited and unsolicited) and with any AE during the solicited follow-up period (Day 0 to Day 6) will be tabulated with exact 95% confidence interval (CI) after each vaccine injection and overall.

The percentage of vaccine injections followed by at least one local AE (solicited and unsolicited), by at least one general AE (solicited and unsolicited) and by any AE will be tabulated, overall vaccination course, with exact 95% CI.

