#### 5.3.2.7. Concomitant medications

Template Table R - 14

Incidence of concomitant medication during the 30-day (Days 0-29) post-vaccination period

|  | [Each group] |   |   |    |    |  |  |
|--|--------------|---|---|----|----|--|--|
|  | 95% CI       |   |   |    |    |  |  |
|  | Ν            | n | % | LL | UL |  |  |
| [Each dose] [Overall/dose] [Overall/subject] |              |   |   |    |    |  |  |
| Any  |              |   |   |    |    |  |  |
| Any antibiotic                               |              |   |   |    |    |  |  |
| Any antipyretic                              |              |   |   |    |    |  |  |
| Any immunosuppressant                        |              |   |   |    |    |  |  |

For each dose and overall/subject:

N= number of subjects with at least one administered dose

n/%= number/percentage of subjects who started to take the specified concomitant medication at least once during the mentioned period

For overall/dose:

N= number of administered doses

n/%= number/percentage of doses after which the specified concomitant medication was started at least once during the mentioned period

95% CI = exact 95% confidence interval, LL = Lower Limit, UL = Upper Limit

Data source = Appendix table IIDi

| gsk
GlaxoSmithKline | Study RAP          |                  |  |  |  |
|------------------------|--------------------|------------------|--|--|--|
| Study Id: 108706       | Abbreviated Title: | PRO HIV-005      |  |  |  |
| Version: Draft version | ⊠ Final            | Date: 26SEP 2008 |  |  |  |

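### The footnote to SAP Templates R-3, R-4, R-5 and R-7 gives the per-dose rows the overall/subject denominator, so read literally the dose-2 row includes subjects with no dose-2 data

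*SAP*

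**What the plan says.** Template Tables R-3 (SAP 5.3.2.2), R-4, R-5 and R-7 (SAP 5.3.2.3) report symptoms by dose, over all doses and over all subjects. Their footnotes have two parts. The first covers the each-dose rows and the overall/subject row together and defines "N= number of subjects with at least one documented dose". The second covers the overall/dose row and defines "N= number of documented doses".

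The methods text treats missing solicited data as follows. Protocol 10.6 does not replace missing measurements and says the analysis on the total "vaccinated cohort will include only injections with documented safety data (i.e. symptom screen/sheet completed"). SAP 3.2.2 says that the "cohort will include only subjects/doses with documented safety data".

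Unsolicited events and concomitant medication follow another rule, also in SAP 3.2.2: "all vaccinated subjects will be considered and subjects who did not report an event will be considered as subjects without an event". R-3 mixes the two kinds of event, because SAP 3.2.4 tabulates solicited and unsolicited symptoms together, "after each vaccine injection and overall".

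Template Table R-14 (SAP 5.3.2.7, concomitant medication) has a parallel footnote for its each-dose and overall/subject rows: "N= number of subjects with at least one administered dose".

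**The concern.** The shared definition suits the overall/subject row. It does not suit a row for one particular dose. A subject who had dose 1 documented and then missed the second vaccination, or did not return the second diary, has a documented dose and so meets the definition for the dose-2 row. For solicited symptoms that subject cannot enter the dose-2 numerator, so a missing sheet acts as a symptom-free report. The same would happen in the dose-1 row for a subject with only dose 2 documented.

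Solicited symptoms after each vaccination are a primary endpoint (Protocol 10.1). Any error from this source lowers the reported rate and its exact confidence limits, which is the non-conservative direction for safety. The documents also foresee incomplete courses: Protocol 4.5 and 9.2.2 provide for stopping vaccination, Protocol 9.2 does not replace withdrawals, and Template D-5 has lines for one and for two doses received.

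**Working it through.** No figure in the plan depends on this footnote, so there is nothing to reproduce first. The check compares the definitions and then works out the size of the difference.

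**Inputs**
- Planned group sizes: 50 per adjuvanted group and 10 per non-adjuvanted group (Protocol 6.4).
- Interval: exact two-sided 95% Clopper-Pearson (SAP 3.4).
- Subjects with dose 1 but not dose 2 documented: not given. Assumed 0, 2 or 5 of 50, and 0, 1 or 2 of 10.
- Subjects with the symptom after dose 2: assumed, chosen to give dose-specific rates of about 75-80%.

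**Formula.** Let x be the subjects reporting the symptom after dose 2, D2 those with dose 2 documented, and A those with any dose documented.
- Dose-specific rate = x / D2.
- Rate with the footnote's N taken literally = x / A.
- Ratio of the second to the first = D2 / A, whatever x is.

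**Results (assumed counts)**

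| A | Missing at dose 2 | D2 / A | Dose-specific (95% CI) | Literal N (95% CI) | Difference, points |
|---|---|---|---|---|---|
| 50 | 0 | 1.00 | 40/50 = 80.0% (66.3-90.0) | 40/50 = 80.0% (66.3-90.0) | 0 |
| 50 | 2 | 0.96 | 38/48 = 79.2% (65.0-89.5) | 38/50 = 76.0% (61.8-86.9) | 3.2 |
| 50 | 5 | 0.90 | 36/45 = 80.0% (65.4-90.4) | 36/50 = 72.0% (57.5-83.8) | 8.0 |
| 10 | 0 | 1.00 | 8/10 = 80.0% (44.4-97.5) | 8/10 = 80.0% (44.4-97.5) | 0 |
| 10 | 1 | 0.90 | 7/9 = 77.8% (40.0-97.2) | 7/10 = 70.0% (34.8-93.3) | 7.8 |
| 10 | 2 | 0.80 | 6/8 = 75.0% (34.9-96.8) | 6/10 = 60.0% (26.2-87.8) | 15.0 |

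The ratio does not depend on the symptom rate, but the difference in points does. With 5 of 50 missing and 9 subjects affected, 9/45 = 20.0% becomes 9/50 = 18.0%, a difference of 2.0 points.

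**Reconciliation within one table.** Take 50 subjects, all with dose 1 documented and 5 without dose 2. The literal per-dose Ns are 50 and 50, which sum to 100. The overall/dose row counts documented doses: 50 + 45 = 95. With dose-specific Ns of 50 and 45 the rows agree.

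**R-3.** The multiplier applies cleanly to R-4, R-5 and R-7, which hold solicited symptoms only. In R-3 a subject who received dose 2 but returned no sheet could still have an unsolicited event recorded. Under the rule for unsolicited events that subject belongs in the denominator; under the rule for solicited symptoms the subject does not. No section says which rule sets the per-dose N.

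**R-14.** Concomitant medication follows the all-vaccinated rule, so an N based on at least one administered dose does not conflict with Protocol 10.6. The only mismatch is internal: its overall/dose row counts administered doses, so a dose not given adds nothing there but would still be counted in the dose-2 row.

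**The case against.** The strongest reply is that the footnote was never meant to be read so literally. The definition of n in the same footnotes carries no dose qualifier either. Taken literally for both N and n, the dose-1, dose-2 and overall/subject rows would print the same figures, which cannot be the purpose of separate rows. On a row-by-row reading, the documented dose in the dose-2 row is dose 2 and nothing is wrong. SAP 3.2.2 and Protocol 10.6 already exclude undocumented data, and nothing says that a table shell overrides them.

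This has force: the row-by-row reading is possible and may be what the authors intended. It does not settle the matter. The footnote to Template R-2 separates a count tied to the dose in question from one satisfied by any dose, so the authors made the distinction explicitly elsewhere. The subjects/doses wording in SAP 3.2.2 does not clearly fix the N of a dose-2 row. A programmer working from the shell could defend either denominator.

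Other parts of the reply stand in full. The safety tables are descriptive; the only between-group assessment (SAP 3.3.5.2) concerns CD4+ T-cells, so no reactogenicity test rests on this N. N is printed in each row, and Templates R-1, R-2 and D-5 show documentation and doses received, so a careful reader could detect a discrepancy. SAP 2.5 says the Month 2 analysis has been performed, and the macro code is not in the documents, so the denominator actually used is unknown.

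**Conclusion.** The footnote is wrong as worded for the each-dose rows of R-4, R-5 and R-7, and it leaves the rule for R-3 open. It conflicts with Protocol 10.6 and with the templates' own overall/dose N. If it is followed, the dose-2 rate for a solicited symptom is multiplied by the share of subjects with any documented dose who also have dose 2 documented: 0.96 for 2 of 50 missing, 0.80 for 2 of 10.

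This rests on two conditions that the documents do not establish: that the table macros follow the footnote literally, and that some subjects lack dose-2 documentation. If either fails, there is no effect.

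A reader might infer three stronger things. One is that the reported dose-2 rates are in fact too low; the documents show neither the macros' N nor any count of missing sheets. Another is that comparisons between antigen doses, or of dose 1 with dose 2, are distorted; that would need missingness that differs between groups or doses, for which there is no evidence, and no such test is planned. The third is that R-14 breaks the missing-data rule; it does not, because medication is analysed on all vaccinated subjects.

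The point is worth acting on because it concerns the denominator of a primary safety endpoint and any error would favour the vaccine.

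**What to change.** - In R-4, R-5 and R-7, split the footnote. For each dose, N is the number of subjects who have that dose documented. For overall/subject, keep the present definition.
- In R-3, make the same split and state which missing-data rule sets the per-dose N for the pooled solicited and unsolicited rows.
- Check that the N printed in the Month 2 tables by %FREQ (R-4, R-5, R-7) and %LOCGEN (R-3) is dose-specific. Correct the tables if it is not.
- In R-14, as a minor consistency edit only, let the per-dose rows count subjects to whom that dose was administered.

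The cost is footnote wording in five templates and a check of existing output against the dose-wise counts in R-1, R-2 and D-5. Tables need re-running only if the check fails.
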